# 3.2 Data Collection

#### 3.2.1 Participant enrolment

The randomisation PWA will collect anonymised data relating to the management and initial outcome of the cardiac arrest call. The NCAA (a national clinical audit of in-hospital cardiac arrests in the UK) and/or data collection by research staff at participating sites will provide data on patient and cardiac arrest characteristics.

### 3.2.2 Hospital follow-up

The NCAA and/or data collection by research staff at participating sites will provide data on patient outcomes, supplemented by a small amount of additional data collection using a standardised case report form (CRF) at each site during the patient's hospital stay.

### 3.2.3 Long term follow-up assessments

Consistent with the core outcome set recommendations, health related quality of life will be measured using EQ-5D-5L at discharge/30 days, 3 and 6 months. mRS will also be measured at 3 and 6 months. The EQ-5D-5L captures the timespan over which functional/neurological recovery tends to plateau (43). It is less burdensome to complete than other tools, is freely available, accessible in multiple languages and may be completed by the patient or a proxy. It comprises five dimensions: mobility; self-care; usual activities; pain/discomfort; anxiety/depression. Each dimension has 5 levels: no problems; slight problems; moderate problems; severe problems; extreme problems. From the EQ-5D-5L health utilities will be calculated for all participants, using standard tariffs. A £15 voucher will be given to every participant who completes a questionnaire at 3 months, and again at 6 months, to acknowledge their contribution to the study.

Longer-term follow up: data will be obtained from NHS England Hospital Episode Statistics (for further Emergency Department attendances and hospital admissions up to 6 months post randomisation), the National Cardiac Arrest Audit (for mRS at discharge or 30 days and length of hospital stay) and the Case Mix Programme National Clinical Audit for adult intensive care (for length of ITU stay) to enable efficient, long-term follow-up of patients. Follow-up for post discharge functional outcomes and health related quality of life will be coordinated by the WCTU and use an established system for contacting patients or their personal consultee to ensure effective follow up (rates > 98% in previous studies) (34,35).

# 4. ADVERSE EVENT MANAGEMENT

# 4.1 Definitions

#### 4.1.1 Adverse Events (AE)

An Adverse Event (AE) is defined as any untoward medical occurrence in a participant *participating in a clinical study* and which does not necessarily have a causal relationship with the treatment/intervention.

#### 4.1.2 Serious Adverse Events (SAEs)

A Serious Adverse Event is an AE that fulfils one or more of the following criteria:

• Results in death

- Is immediately life-threatening
- Requires hospitalisation or prolongation of existing hospitalisation
- Results in persistent or significant disability or incapacity
- Is a congenital abnormality or birth defect
- Immediate intervention was required to prevent one of the above or is an important medical condition.

#### 4.2 Assessing and reporting AEs, SAEs, ADEs, SADEs and related SAEs

The assessment and reporting of AEs, SAEs and related SAEs will follow the relevant Warwick CTU SOPs. This trial is comparing two interventions that are already in routine use in NHS clinical practice and which will be used in accordance with manufacturer's instructions.

All patients in this trial will be in an immediately life-threatening situation; many will not survive, and all of those who do will be hospitalised, with the majority of survivors admitted to intensive care. These situations are therefore anticipated as a result of the condition, and events leading to any of them should only be reported as an SAE if their cause was clearly separate from the cardiac arrest. Events that are related to cardiac arrest and would be expected in patients undergoing attempted resuscitation (including death and intensive care admission) should not be reported. Clinical details about these events will be routinely collected in the case report form as part of the trial outcomes.

Events should be reported as a serious adverse event only if they:

- occur between randomisation and hospital discharge
- are serious AND are potentially related to trial participation, i.e. may have resulted from study treatment such as use of a SGA or TI;

#### AND

• are unexpected, i.e. the event is not an expected occurrence for patients who have had a cardiac arrest and received advanced airway management.

Examples of events that should not be reported as SAEs because they are anticipated following IHCA:

- death
- brain injury
- ITU admission
- aspiration pneumonia

Examples of events that may be SAEs are;

- use of one of the interventions causing a new injury that endangers the patient,
- unrecognised oesophageal intubation,

Adverse events should be recorded on the case report form. Events that meet criteria for seriousness should be reported to WCTU Quality Assurance Team and the sponsor within 24-hours of becoming aware of the event.

Once an adverse event or serious adverse event has been identified, the participant should continue to be followed-up until resolution of the event or a final outcome has been reached.

Following reporting of a serious adverse event, any change of condition or other follow-up information should be sent to the WCTU Quality Assurance team and sponsor as soon as is practicably possible.

The trial manager will liaise with the investigator to compile all the necessary information. The trial coordinating centre is responsible for reporting any related and unexpected SAEs to the sponsor and REC within required timelines. All other recruiting sites in the trial will be informed of the event and any implications for the trial.

The causality of SAEs (i.e. relationship to trial intervention- see table) will be assessed by the investigator(s) on the SAE form (see table).

Relationship to trial intervention	Description
Unrelated	There is no evidence of any causal relationship
Unlikely to be related	There is little evidence to suggest there is a causal relationship (e.g. the event did not occur within a reasonable time after administration of the trial intervention). There is another reasonable explanation for the event (e.g. the patient's clinical condition, other concomitant treatment).
Possible relationship	There is some evidence to suggest a causal relationship (e.g. because the event occurs within a reasonable time after administration of the trial intervention). However, the influence of other factors may have contributed to the event (e.g. the patient's clinical condition, other concomitant treatments).
Probable relationship	There is evidence to suggest a causal relationship and the influence of other factors is unlikely.
Definitely related	There is clear evidence to suggest a causal relationship and other possible contributing factors can be ruled out.

All SAE reports will be reviewed on receipt by the Chief Investigator (or their delegate) for an independent causality assessment and those that are considered to satisfy the criteria for being possibly related, probably related or definitely related to trial interventions (either by the PI or CI) and which are not exempt from reporting will be assessed for expectedness by the CI or a clinical delegate. SAEs that are deemed to be unexpected and related to the intervention will be notified to the REC and sponsor within 15 days of receipt in accordance with regulatory requirements. All such events will be reported to the Sponsor, Trial Steering Committee and Data Monitoring Committee at their next meetings. Reports of all SAEs by randomisation arm will also be reviewed by the DMC at their regular meetings, or more frequently if requested by the DMC Chair.

Adverse Device Events and Serious Adverse Device Events

In the event of problems with a device in use we will notify the MHRA in accordance with WCTU SOP 17, part 2.

Examples of ADEs and SADEs include:

- malfunction of the device causing injury to the clinical team,
- malfunction of the device leading to inadequate patient ventilation.

#### 4.3 Responsibilities

#### Principal Investigator (PI):

Checking for AEs when participants are reviewed or followed-up.

- 1. Using medical judgement in assigning seriousness and causality
- 2. Ensuring that all SAEs are recorded and reported to the Sponsor within 24 hours of becoming aware of the event and provide further follow-up information as soon as available. Ensuring that SAEs are chased with Sponsor if a record of receipt is not received within 2 working days of initial reporting.
- 3. Ensuring that AEs are recorded and reported to the Sponsor in line with the requirements of the protocol.

#### Chief Investigator (CI) / delegate or independent clinical reviewer:

- 1. Clinical oversight of the safety of patients participating in the trial, including an ongoing review of the risk / benefit.
- 2. Using medical judgement in assigning causality
- 3. Immediate review of all related and unexpected SAEs
- 4. Review of specific SAEs in accordance with the trial risk assessment and protocol as detailed in the Trial Monitoring Plan.
- 5. Production and submission of annual reports to the relevant REC.

#### Sponsor or delegate:

- 1. Central data collection and verification of AEs, and SAEs, according to the trial protocol.
- 2. Expectedness assessment of related SAEs
- 3. Reporting safety information to the CI, delegate or independent clinical reviewer for the ongoing assessment of the risk / benefit according to the Trial Monitoring Plan.
- 4. Reporting safety information to the independent oversight committees identified for the trial (Data Monitoring Committee (DMC) and / or Trial Steering Committee (TSC)) according to the Trial Monitoring Plan.
- 5. Expedited reporting of related and unexpected SAEs to the REC within required timelines.
- 6. Notifying Investigators of related and unexpected SAEs that occur within the trial.

#### Trial Steering Committee (TSC):

In accordance with the Terms of Reference for the TSC, periodically reviewing safety data and liaising with the DMC regarding safety issues.

#### Data Monitoring Committee (DMC):

In accordance with the Terms of Reference for the DMC, periodically reviewing unblinded overall safety data to determine patterns and trends of events, or to identify safety issues, which would not be apparent on an individual case basis.

#### 4.4 Notification of deaths

Death is collected as a study outcome. No separate notification of death is required.

#### 4.5 Reporting urgent safety measures

If any urgent safety measures are taken the CI/Sponsor will immediately and in any event no later than 3 days from the date the measures are taken, give written notice to the relevant REC of the measures taken and the circumstances giving rise to those measures, in accordance with Warwick SOPs.

# 5. DATA MANAGEMENT

Personal data collected during the trial will be handled and stored in accordance with UK GDPR and Warwick SOPs. Due to the need to link data across datasets, approval to hold confidential data without consent will be sought from the Health Research Authority Confidentiality Advisory Group (CAG).

Personal identifiable data will be held separately to trial data on the trial database, with linkage provided through a unique trial number. The trial database is encrypted and held on a secure server at the University of Warwick. Access to the table containing patient identifiable data will be restricted to members of the trial team who require access, i.e., only those undertaking data linkage work and contacting patients for follow up.

#### 5.1 Data collection and management

Data management processes will be documented in a Data Management Plan. Case Report Forms (CRFs) entered directly on to the database and a Progressive Web Application (PWA) will be developed to collect all required trial data. Central monitoring will occur at each site for quality purposes. Full site monitoring will be triggered if a significant error rate is found, which is outlined in the Data Management Plan. In addition, the first set of recruitment data collected from all new sites will be scrutinized.

**Hospital admission through to discharge:** The PWA will collect data at randomisation, including data related to the management and initial outcome of the cardiac arrest call. The National Cardiac Arrest Audit (NCAA) is a national clinical audit of in-hospital cardiac arrests in the UK. The NCAA database and/or data collection by research staff at participating sites using a standardised case report form (CRF) will be used to collect patient characteristics, cardiac arrest characteristics, and patient outcomes. Identifiable data will be collected on a CRF by the hospital clinical and research team for data linkage purposes.

**Post discharge and long term follow-up (3 and 6 months)**: Consistent with the core outcome set recommendations, modified Rankin Scale and health related quality of life using EQ-5D-5L will be measured at 3 and 6 months. Following confirmation of survival status, participants will be followed up at 3 and 6 months and asked to complete these two questionnaires. The patient may opt to complete these questionnaires by post, online or by telephone according to their preferences, and will be given a £15 voucher at each time point to acknowledge their contribution. If the participant

lacks capacity then a consultee may complete the questionnaires on their behalf. If the participant or consultee cannot be reached after 3 contact attempts no further attempts will be made on that occasion, however if they do not respond after 3 contact attempts at 3 months a further contact will be made (on up to 3 occasions) at 6 months.

**Longer-term follow up:** Data will be obtained from NHS England Hospital Episode Statistics, the National Cardiac Arrest Audit (NCAA) and the Case Mix Programme National Clinical Audit to enable efficient, long-term follow-up of patients up to 6 months. Data sharing agreements will be in place for each organisation involved in data linkage to cover the sharing of personal data. Follow-up for post discharge functional outcomes and health related quality of life will be coordinated by the WCTU and use an established system for contacting patients or their legal representatives to ensure effective follow up.

#### 5.2 Database

The database will be developed by the Programming Team at WCTU and all specifications (i.e. database variables, validation checks, screens) will be agreed between the programmer and appropriate trial staff.

### 5.3 Data storage

All essential documentation and trial records will be stored by WCTU and recruiting sites in conformance with the applicable regulatory requirements and access to stored information will be restricted to authorised personnel. Study documents (paper and electronic) will be retained in a secure location during and after the study has finished. All essential documents, including patient records and other source documents will be retained for a period of 5 years following the end of the study. Where study related information is documented in the hard copy medical records – those records will be identified by a 'Do not destroy before dd/mm/yyyy' label where date is 5 years after the last patient last visit. Where electronic records are in use, trust policy will be followed.

# 5.4 Data access and quality assurance

All data access will be controlled by individual usernames and passwords and any changes to data will require the user to enter their username and password as an electronic signature in accordance with regulatory requirements. Staff will have access restricted to the functionality and data that are appropriate for their role and responsibilities in the study documented on the central coordinating delegation log. Any data that are transferred out of the secure environment (for example for statistical analysis) will adhere to Warwick SOPs.

# 5.5 Data Shared with Third Parties

The trial statisticians and DMC will have access to the dataset for the analysis of trial outcomes. Once the main analyses have been undertaken, de-identified individual participant data will be available to other investigators subject to approval of data analysis plans and compliance with the University of Warwick SOPs on Data Management and Sharing. Approval of data analysis plans will be the responsibility of the TSC during the lifetime of the trial. Following study completion, the Chief Investigator and WCTU Data Sharing Committee will be jointly responsible for the approval of data analysis plans. The trial will comply with Data Sharing Policies that may be instituted by the NIHR during the lifetime of the project.

# 5.6 Archiving

Trial documentation and data held at Warwick Clinical Trials Unit that is required for reconstruction of the study results will be archived for at least 5 years from the close of the study. The trial master file and associated data will be archived by WCTU. All personal data for which there is no longer a purpose to hold will be removed at the point at which it is no longer required. An anonymised data set will be held indefinitely after the 5 year period, to allow for data sharing and maximise benefit. This will be included in the participant information sheet and consent form.

The local Principal Investigators will maintain all records and documents regarding the conduct of the study. Where study related information is documented in the hard copy medical records – those records will be identified by a 'Do not destroy before dd/mm/yyyy' label where date is 5 years after the last patient last visit. Where electronic records are in use, trust policy will be followed. These will be archived by the site for at least 5 years or for longer if required. If the responsible investigator is no longer able to maintain the study records, a second person will be nominated to take over this responsibility.

# 6. STATISTICAL ANALYSIS

### 6.1 Power and sample size

To identify a clinically significant difference of 3% (8.5% vs. 11.5%) in the primary outcome requires 4,190 patients (2,095 per group) at the 5% level for statistical significance and 90% power.

The primary outcome is the modified Rankin Scale score (mRS), which is a 7-point scale that is widely used in cardiac arrest research and often dichotomized into 0-3 versus 4-6 categories, with 0-3 score categories approximating the proportion of patients with a 'good' functional outcome and 4-6 score categories approximating the proportion of patients with a 'poor' functional outcome at hospital discharge (21,22).

Survival to hospital discharge is 24% among all IHCA patients, but additional analysis of these audit data suggest that survival may be as low as 10% in those receiving TI (9). This is because cardiac arrests of a shorter duration are both less likely to require advanced airway management and less likely to have a poor outcome (12,18). The sample size is based on mortality, for which data are available. This is not identical to our primary outcome (for which data are not available), however the mRS is dominated by mortality (score 6) in this population, because the fatality rate approaches 90%.

In terms of the clinically relevant difference, the best available observational evidence shows an absolute difference in survival to discharge of 3.1% (19.4% vs. 16.3%) favouring alternatives to TI (10). Our recent national survey demonstrated that current practice is a mixture of TI and SGA use (9), and it is therefore assumed that the baseline survival of 10% comprises an equal mix of TI and SGA patients. The 3% minimum clinically significant difference around this baseline of 10% has been set accordingly (8.5% vs. 11.5%). To demonstrate this effect size of 3% difference (8.5% to 11.5%) in patients with a 'good' functional outcome between the interventions, requires a total sample of 4,190 patients (90% power; type I error 5%).

# 6.2 Statistical analysis of efficacy and harms

#### 6.2.1 Statistics and data analysis

The primary statistical analysis will be by intention to treat amongst those randomised to TI versus SGA. The primary outcome rate will be assessed using a mixed-effects logistic regression model with hospital site as a random effect and adjustment for pre-defined important fixed covariates. These

covariates will be included in the analysis plan, prior to any analysis. Secondary outcomes which are categorical will be analysed in a similar way (using mixed-effects logistic regression models). For continuous outcomes, we will assess the distribution of the data and use appropriate analytical methods – if the data is normally distributed we will use mixed-effects linear regression models and if it is non-normal we will use log transform of the data or the gamma distribution to model the data. Results will be reported using odds ratio or mean difference with 95% confidence intervals.

Crossover: Crossover will be assessed in two ways:

(i) impact on the statistical power of the study: due to the contamination effect in patients who crossover from one intervention to another, there is likely to be a reduction in the study power. We will examine the loss of power, using power curves and different degrees of crossover, pivoted around the observed crossover rates(38), and assess this at the end of the pilot study as well as presenting these to the DMC at each 6-monthly analysis.

(ii) for the final analysis, we will use inverse probability weighted (IPW) analysis to account for crossovers, using the primary outcome measure.

#### **INTERNAL PILOT**

The main trial will be preceded by an internal pilot study of 6 months duration. This will follow the same processes as the main trial, and all patients recruited to the pilot study will be included in the final analysis. The pilot will take place in 40 representative sites to confirm recruitment rates, protocol compliance and data collection, and will aim to recruit 420 patients representing 10% of the total study sample.(36) In particular, we will audit: (a) screening data; (b) recruitment; (c) reasons for exclusion; (d) protocol adherence, crossovers and fidelity to the intervention; (e) implementation of the training and protocol into practice, using screening logs, case report forms (CRFs) and virtual site visits. We will also review the assumptions on which the sample size calculation is based.

The recruitment rate during the pilot study is shown in the recruitment section.

	Red	Amber	Green			
RECRUITMENT						
% Threshold	<60%	60-99%	100%			
Sites recruited	<25	26-39	40			
Total number of participants recruited	<252	252-419	420			
COMPLIANCE/ADHERENCE (of those recruited)						
% Threshold	<75%	75-85%	86-100%			
Total number of participants compliant	<180	180-305	306-420			

Trial progression criteria will be:

Success criteria for recruitment will be (a) 100% recruitment: progress to main trial; (b) 60-99% recruitment: progress to main trial with review of screening log and protocol, adjustments to the protocol and research processes as required and explore the possibility of additional sites; (c) less than 60% recruitment: progression to main trial not anticipated.

Success criteria for protocol adherence and fidelity to the intervention: (a) 86-100% adherence: progress to main trial; (b) 75-85% adherence: progress to main trial with intensive efforts to improve adherence informed by learning from pilot sites; (c) < 75% adherence: progression to main trial not anticipated.

These criteria will be reviewed by the Data Monitoring and Ethics Committee (DMC) and the Trial Steering Committee (TSC) in association with the HTA secretariat.

On reaching the pre-defined success criteria, the internal pilot will run seamlessly into the main trial. The pilot study results will be reported in the HTA Monograph in accordance with the CONSORT guideline for pilot studies (37).

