#### 2.8 Randomisation

#### 2.8.1 Randomisation

The randomisation algorithm will be provided by Warwick Clinical Trials Unit (WCTU). A computergenerated randomisation sequence will be created, stratified by hospital site and time of day (8am to 6pm or outside of these hours). Time of day is included as a stratification variable because out-ofhours cardiac arrests tend to have less favourable outcomes (42). Patients will be randomised 1:1 to SGA or TI. Randomisation will take place using a bespoke mobile phone progressive web application (PWA), which will be developed by the programming team at WCTU. The PWA will function asynchronously (off-line) to address any problems with data connectivity that may exist in participating hospitals, and to ensure there is no delay in the randomisation process. If the patient is deemed eligible pressing a single button on screen will immediately display the allocation, and irrevocably enrol the patient. If, due to a technical or other failure, the PWA does not display an allocation within five seconds the patient will be treated according to usual care and the clinical judgement of the cardiac arrest team. If, despite technical failure, the allocation is recorded by the PWA the patient will be included in the study under the "intention to treat" principle, whereas if no allocation is recorded the patient will not be included in the study. Following the IHCA a small additional amount of non-identifiable patient data will be entered to the PWA by the enrolling clinician and automatically uploaded to WCTU. WCTU will then alert the research team at that hospital site for patient identification and follow-up. Preparatory work by the trial team including interviews and simulations has demonstrated that this approach is clinically and technically feasible; it will be tested further during the internal pilot study.

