# 2.9 Trial treatments / intervention

#### 2.9.1 Trial treatment(s) / intervention

Intervention: A **supraglottic airway device** of the type used routinely in that hospital. During resuscitation the SGA will be placed according to manufacturer's instructions, with end-tidal carbon dioxide monitoring wherever possible, following an initial period of bag-mask ventilation as required. If a functioning SGA has already been placed at the point of randomisation, and the patient is randomised to SGA, this device may be left in situ. Two attempts at SGA placement should be made. An attempt is defined as introducing a SGA past the teeth, and concludes when the SGA is removed from the mouth. If two attempts at SGA placement are unsuccessful treatment will proceed as dictated by the treating clinician (including tracheal intubation if indicated). If successful, the SGA should be used until resuscitation efforts cease or return of spontaneous circulation (ROSC) is achieved for >20 minutes, at which point further management will proceed as dictated by the treating clinician.

Comparator: **Tracheal intubation.** During resuscitation tracheal intubation should occur, with endtidal carbon dioxide monitoring wherever possible, following an initial period of bag-mask ventilation as required. If a functioning SGA has already been placed at the point of randomisation, and the patient is randomised to tracheal intubation, the SGA should be removed, and tracheal intubation attempted. Two attempts at intubation should be made. An attempt is defined as introducing the laryngoscope past the teeth and concludes when the laryngoscope is removed from the mouth, regardless of whether or not a tracheal tube is inserted. If two attempts at tracheal intubation are unsuccessful subsequent treatment will proceed as determined by the treating clinician (including placement of a SGA if indicated). If successful, tracheal intubation should continue until resuscitation efforts cease or ROSC is achieved for >20 minutes, at which point further management will proceed as dictated by the treating clinician.

Both interventions are part of standard clinical care in the treatment of IHCA and there are no known additional risks to the participants above routine care.

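### The pilot's adherence criterion pools the two arms, so it can hide poor delivery of tracheal intubation, and its count row contradicts its percentage row

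*Protocol*

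**What the plan says.** The Internal Pilot part of Protocol 6.2.1 "will aim to recruit 420 patients representing 10% of the total study sample". Its adherence block is headed "COMPLIANCE/ADHERENCE (of those recruited") and has a single line, "Total number of participants compliant".

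| | Red | Amber | Green |
|---|---|---|---|
| Percentage row | <75% | 75-85% | 86-100% |
| Count row | <180 | 180-305 | 306-420 |

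The text below the table repeats the percentages: "Success criteria for protocol adherence and fidelity to the intervention: (a) 86-100% adherence: progress to main trial", and at the lower end "< 75% adherence: progression to main trial not anticipated". Amber means progressing with intensive efforts to improve adherence. Green means running straight into the main trial. No threshold is set by arm, and adherence is not defined.

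Section 2.8.1 states: "Patients will be randomised 1:1 to SGA or TI". Section 2.9.1 treats the arms differently when a working SGA is already in place. If "the patient is randomised to SGA, this device may be left in situ"; if the allocation is TI, "the SGA should be removed, and tracheal intubation attempted". Section 2.5 expects an SGA before randomisation in some centres, with bag-mask ventilation as the usual case. Section 1.2 describes SGAs as generally quicker and easier to insert.

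**The concern.** The pilot has to show that both allocated treatments can be delivered. The protocol itself gives reasons to expect adherence to be easier in one arm, so an average over arms is a weak test of the harder one. Where the SGA arm does well, it offsets a shortfall in TI delivery, and the colour can come out better than the TI arm alone would earn. What is then lost is the prescribed reaction: the corrective effort attached to amber, or the reconsideration attached to red.

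This matters beyond the count of deviations. Section 2.9.2 warns that crossover may be selective by prognosis. One-sided switching from TI to SGA would blur the comparator and place more weight on the inverse-probability-weighted analysis of 6.2.1.

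Two further features of the text add to the problem. The count row does not match the percentages. Section 6.5, in explaining its exclusions, calls it clinically inappropriate to take out a functioning advanced airway device because of enrolment, while 2.9.1 directs removal of a working SGA in the TI arm. While both statements stand, staff have a reason within the protocol not to deliver TI.

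**Working it through.** **Inputs.** Pilot of 420 patients and limits of 75% and 86% (Internal Pilot, 6.2.1); 1:1 allocation (2.8.1), hence about 210 per arm; 8.5% against 11.5% with 2,095 per arm (6.1). All by-arm adherence rates below are assumptions.

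**1. The plan's own counts.** 86% of 420 = 361.2 and 75% of 420 = 315. The table has 306 and 180. 306/420 = 72.9% and 180/420 = 42.9%. No single denominator explains both: 180/0.75 = 240, while 306/0.86 = 355.8 (306 is 85% of 360). The band's upper end of 420 shows that 420 is the intended denominator. The counts do not reproduce.

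**2. Green by percentage with TI below 75%.** Pooled green needs at least 362/420 (86.2%). TI below 75% means at most 157/210.
- Lowest TI: 362 - 210 = 152, i.e. 152/210 = 72.4%, with SGA at 100%.
- Lowest SGA: 362 - 157 = 205, i.e. 205/210 = 97.6%, with TI at 157/210 = 74.8%.

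The window is TI 72.4-74.8% with SGA 97.6-100%. If 361/420 (85.95%) is rounded up to 86%, the window widens by one patient.

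**3. Green by count.** 306 - 210 = 96, so green is possible with TI at 96/210 = 45.7%.

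**4. Probabilities of the pooled colour.** The total is the sum of two binomials, Bin(210, SGA rate) + Bin(210, TI rate). By percentage, green is 362 or more and red is 314 or fewer.

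| Assumed SGA / TI | Expected pooled | Green by % | Red by % | Green by count |
|---|---|---|---|---|
| 100% / 72% | 86% | 0.49 | 0.00 | 1.00 |
| 98% / 72% | 85% | 0.26 | 0.00 | 1.00 |
| 95% / 72% | 83.5% | 0.07 | 0.00 | 1.00 |
| 95% / 78% | 86.5% | 0.61 | 0.00 | 1.00 |
| 95% / 60% | 77.5% | 0.00 | 0.08 | 0.99 |

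**5. The same limits by arm.** 0.75 x 210 = 157.5 and 0.86 x 210 = 180.6, so red is 157 or fewer and green is 181 or more, with the lower arm deciding.
- 95%/78%: green 0.002, red 0.15, otherwise amber.
- 95%/60%: red with probability above 0.99.
- 86%/86%: green 0.27 (0.49 pooled); red about 0.00002.
- 88%/88%: green 0.67 (0.89 pooled).

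**6. Precision.** 95% half-width at 86%: 1.96 x sqrt(0.86 x 0.14/210) = 4.7 points by arm; with 420, 3.3 points.

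**7. Does pooling cost power?** The planned 8.5% against 11.5% with 2,095 per arm gives 89.9%, which reproduces the stated 90%. Assume every non-adherent patient receives the other device.
- 86%/86%: TI 8.5 + 0.14 x 3 = 8.92%; SGA 11.5 - 0.14 x 3 = 11.08%; difference 2.16 points; power 64%.
- 100%/72%: TI 8.5 + 0.28 x 3 = 9.34%; SGA 11.5%; difference 2.16 points; power 63%.

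The loss depends on total non-adherence and hardly at all on how it is split between arms.

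**The case against.** Much of the case on the other side stands.

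- **The extreme case is narrow.** A reader might infer that the trial could easily turn green while TI adherence is below 75%. By the percentage row it could not: SGA at 95% and TI at 72% gives green only 7% of the time.
- **The 75% line is defined for the total only.** Speaking of the TI arm as red extends the rule. The stated consequence is that progression is not anticipated, which is softer than a stop.
- **High SGA adherence is not documented.** The protocol gives no frequency for an SGA already in place. Return of circulation before any airway attempt (2.8.2) can occur in either arm. If it counts as non-adherence, 97.6% is hard to reach.
- **Adherence is not the same as intubation.** After two failed attempts 2.9.1 leaves management to the clinician, including an SGA, so a patient never intubated may still be adherent. Conversely, non-adherence need not be crossover, so full crossover in step 7 is an upper-end assumption.
- **Power.** A reader might blame pooling for a fall to about 63%. Step 7 shows that the loss comes with 86% adherence overall.
- **Crossover is watched elsewhere.** Sections 2.9.2, 6.2.1, 6.4 and 7.11 provide monitoring, training, power curves and compliance reports to the DMC.

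These points limit the size of the problem but do not remove it. None of the monitoring provisions sets a trigger by arm, and a power curve cannot tell 86%/86% from 100%/72%. The count-row contradiction does not depend on any assumption about the arms.

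**Conclusion.** The point holds as a weakness in a stated decision rule. The pooled criterion can hide poor TI delivery, chiefly in two moderate ways: green while TI is in the amber range (0.61 at 95%/78%), or amber while TI is far below 75% (pooled red only 0.08 at 95%/60%). Green with TI below 75% is a narrow possibility by percentage and a wide one by count, down to 45.7%.

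The count row is an outright inconsistency: 306/420 is green by count and red by percentage.

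The probabilities rest on assumed by-arm rates, 210 patients per arm, independent binomial outcomes and the plan's limits extended to each arm. The documents do not show how often masking would occur, and they do not support attributing a loss of power to pooling.

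**What to change.** In the Internal Pilot part of 6.2.1:

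1. Correct the count row to the percentages, which the text states twice. For 420 patients: red 314 or fewer, amber 315-361, green 362 or more. Say how values between 85% and 86% are classed.
2. Define adherence, including how return of circulation before any airway attempt and two failed attempts are counted.
3. Apply the 75% and 86% limits to each arm, with the lower arm setting the colour. For 210 per arm: red 157 or fewer, amber 158-180, green 181 or more. The DMC and the TSC both keep their review of the criteria.
4. Show on a separate line the SGA-arm patients whose device was already in place at randomisation, so that adherence by default is visible.
5. Use the same by-arm measure in the 6-monthly crossover reports to the DMC.

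Sections 2.9.1 and 6.5 on removing a functioning airway device must also be reconciled by those responsible for the clinical content.

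The drafting cost is a few sentences and table rows. The statistical cost is a by-arm interval of about ±4.7 points instead of ±3.3, and more amber results when both arms are near the limit: at true 86% in both, green falls from 0.49 to 0.27, with almost no added risk of red. A TI arm truly at 78% would be classed red about 15% of the time, so the committees should read the rates with their intervals.
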